6.4 Retention

Once a participant is enrolled in the study, the study team will make all reasonable efforts to retain her in follow-up to minimize bias associated with loss to follow-up. The study team will track retention rates and address any issues related to retention. Strategies will include:

- Thorough explanation of the study visit schedule and procedures during informed consent, and re-emphasis at each study visit.
- Encouragement of participants to discuss potential study participation with their husbands/partners and other influential family members before agreeing to enrol in the study.
- Collection of detailed locator information at screening, and review and updating of this information at each study visit.
- Use of appropriate and timely visit reminder mechanisms (including phone calls and text messages).
- Mobilization of trained outreach workers to complete in-person contact with participants at their homes and/or other locations.

6.5 Safety monitoring

At each study visit, study staff will evaluate participants for social harms and adverse events (AEs). A social harm will be defined as a non-medical untoward consequence of study participation, including: difficulties in personal relationships, stigma, or discrimination from family or community. An AE will be defined as any untoward medical occurrence in a study participant including any abnormal sign (e.g., abnormal physical exam or laboratory finding),

symptom, or disease, temporally associated with the individual's participation in the research, whether considered related to participation in the research or not. In addition to events related to study procedures, which are expected to be very rare, we can expect that this population of pregnant women will experience adverse events unrelated to study procedures, including adverse obstetrical outcomes, infections, side effects from routine medications, hospitalization, and death.

We expect events to be minimal, but all will be documented, assessed for seriousness / severity and relatedness, and carefully monitored. The severity of study-related adverse events and social harms will be graded using the National Institute of Health's Division of AIDS Table for Grading the Severity of Adult and Pediatric Adverse Events; this is standard of care for all studies conducted at our sites. We will also record information on all serious adverse events (SAEs) occurring in maternal participants whether or not they are related to study participation, including AEs that:

1. Result in hospital admission (unless hospitalization is preplanned, i.e., for delivery) or prolongation of existing hospitalization,
2. Are immediately life-threatening,
3. Cause significant, persistent, or permanent harm or disability, either physical or psychological,
4. Result in death, including fetal demise after 20 weeks of gestation, or
5. Are congenital anomalies/birth defects.

Information on adverse events or social harms that are related to the study and all SAEs will be documented on study data forms and routinely reported to the Principal Investigator (PI) or designee. If the PI, co-investigators, or their designees determine that study-related AEs are occurring at an unexpected rate, they will assess the need for and facilitate staff re-training, protocol amendment, or study cessation. Serious study-related AEs will be reported to all regulatory bodies and the study sponsors within 72 hours of site awareness. Other events will be reported according to each ethics committees' individual guidelines.

6.5.1 Identification and management of clinical complications of pregnancy

When collecting data or performing physical exams, study staff may identify medical or other issues requiring follow-up, treatment, or other clinical care. Similarly, during the course of performing ultrasound procedures on study participants, sonographers may identify medical issues requiring follow-up, treatment, or other clinical care. All team members will be trained on the recognition of adverse events and social harms and what to do if encountered. Safety issues requiring follow-up will be brought to the attention of the senior clinical staff, who will make referrals if the issue is beyond staff knowledge or skills to be able to adequately address.

Potential reasons for clinical referral include, but are not limited to:

- Draining of fluid or concern for ruptured membranes
- Vaginal bleeding or concern for threatened abortion or antepartum hemorrhage
- Abnormal vaginal discharge
- Hypertension
- Fetal anomalies
- Abnormalities of fetal growth
- Oligo- or polyhydramnios
- Intrauterine embryonic or fetal demise

- Malpresentation at or near term
- Suspected extrauterine pregnancy (ectopic)

When possible, the participant will be invited to remain in the study. Additional ultrasound follow-up procedures as determined by obstetrical management recommendations will be provided by study sonographers as requested and free of charge.

6.6 Biological specimen collection

All samples will be obtained from study participants by trained clinical staff according to approved standard operating procedures. Biological samples (i.e., blood and urine) will be used for untargeted metabolomics and other multi-omic analyses to identify metabolites, proteins, transcripts, and host genetic factors associated with fetal maturation, gestational age, parturition timing, and adverse outcomes. Each study site will house its own biological samples and make plans for off-site redundancy in case of power failures or freezer malfunction. Lab testing will be conducted in parallel with the primary analysis and will take advantage of the excellent gestational age dating available for all participants and the even distribution of sample collection across the gestational age spectrum.

Use of stored specimens for testing that is not specifically designated in this protocol as described above will require additional regulatory approval. Separate written informed consent for specimen storage and future use will be specifically obtained during the informed consent process.

6.6.1 Quality control and quality assurance procedures

Standard Operating Procedures (SOPs) following manufacturer's protocols and detailing technical procedures involved (e.g., sample collection, processing, and storage) will be developed and used by the study team. Site coordinators will complete annual recertification. The certification process is an opportunity to ensure the highest specimen quality and standardize collection techniques.

6.7 Data security and management

Research data will be captured in a dedicated study database. Study data management (e.g., data transmission, query resolution, etc.) will follow procedures outlined in study SOPs. Study identification numbers will be used on all forms and communications related to the study. A separate confidential register will link study identification numbers and participants' names. All data instruments and registers will be securely stored. All study computers and electronic devices will be password protected and their access restricted to authorized study personnel. Backups of the data will be made routinely. Data may be transmitted electronically to the study investigators through secure servers. Study information will not be released without written permission of the participant, except when necessary for monitoring by the relevant ethical committees or their designees.

Identifiable data will be maintained for at least ten years after completion of participant follow-up. Biological specimens will be incinerated after ten years from collection or as dictated by in-country guidelines. Study records will be disposed of following sponsor guidelines after being stored in-country for at least three years following the end of study follow-up. Paper records will be destroyed (e.g., shredded or incinerated) prior to disposal.

6.8 Statistical considerations

6.8.1 Study outcomes

The primary study outcome is diagnostic accuracy, measured as difference in mean absolute error (MAE) of the index test and clinical reference standard in the primary evaluation window. MAEs will be calculated as the average of the absolute differences between the GA estimated by the index test (i.e., the FAMLI Technology interpreting blind sweep data generated by an untrained operator with a low-cost probe) or clinical reference standard (i.e., standard fetal biometry performed by a trained sonographer on a commercial ultrasound machine) and previously established ground truth GA.

[figure not shown]
Secondary study outcomes will be assessed for both the index test and clinical reference standard and include (1) MAE in the secondary evaluation windows; (2) root mean squared error (RMSE) in all three evaluation windows; and (3) proportion of studies correctly classified within 7 days of the ground truth.

Secondary lab outcomes will be assessed for all participants. Untargeted metabolomics will investigate organic acids, organoheterocyclic compounds, lipids and lipid-like molecules, benzenoids, organic oxygen compounds, and other minor chemical classes potentially associated with gestational age. Other multi-omics markers including proteins, transcripts, and host genetic factors may also be analyzed.

6.8.2 Sample size calculations

We designed this diagnostic accuracy study to test a non-inferiority hypothesis, such that if we observe a 95% confidence interval (CI) to be *completely* contained in the interval $(-c, c)$ then we declare non-inferiority (or equivalence to bound c), with type 1 error 2.5%. We chose a sample size such that the statistical power for the non-inferiority hypothesis test is 95%. One implication of choosing the above type 1 error and statistical power for this non-inferiority test is that, if we observe the 95% CI to *not* be contained in the interval $(-c, c)$, i.e., the lower end of the observed 95% CI is smaller than $-c$ or the upper end is larger than c , then we may declare superiority, with type 1 error 5%, because the null hypothesis for superiority (i.e., a 0-difference) would be excluded from this observed 95% CI.

We used Monte Carlo simulation to find the sample size that yields a statistical power of at least 95% for the non-inferiority test with type 1 error of 2.5%, and non-inferiority bound of $c = 2$ day error in estimated GA. The statistical test is based on a difference in mean absolute error (MAE), comparing the FAMLI Technology to standard biometry, with both approaches measured in the primary evaluation window, which is between $14\frac{0}{7}$ and $27\frac{6}{7}$ weeks of gestation, inclusive (Figure 6). We chose this window for our primary evaluation because it corresponds to the second trimester of pregnancy, when most women

[figure not shown]
first present in low-resource settings (Figure 7). Both the FAMLI Technology-estimated GA and standard biometry calculate absolute error with respect to the enrollment “ground truth” estimated GA, which is assigned by first trimester ultrasound or, in the case of *in vitro* fertilization, a known embryo age and transfer date.

[figure not shown]
We used women enrolled in the ZAPPS cohort with estimated GA < 13 weeks ($n = 105$) to inform the distribution of enrollment GAs, and another ZAPPS estimated GA measured in the 14 to 27-week window to inform the distribution of primary evaluation EGAs, by the standard approach. The enrollment estimated GA by standard biometry (intergrowth formula) was 74.5 ± 10.5 days. The follow up estimated GA in the primary evaluation window, also obtained by standard biometry (Intergrowth formula), was 155.4 ± 6.1 days, and after adjustment (subtracting the number of days between enrollment and primary evaluation) was 75.6 ± 12.3 days. The observed regression function for the adjusted estimated GA during the primary evaluation window was $-7 + 1.1$ (enrollment estimated GA) ± 4 days. Estimates below are based on 2000 simulations, which yields simulation error less than 2% for statistical power.

We assume the GA estimate produced by the FAMLI Technology has properties (i.e., intercept and slope) similar to standard biometry, but reduces the random error (τ). In a sensitivity analysis, we assumed the FAMLI Technology estimate also removed bias (i.e., intercept 0, slope 1), which yields a slight increase in power (results not shown). We do not anticipate that the FAMLI Technology will induce bias over the standard approach. We vary the random error τ for the FAMLI Technology from $\tau = 1$ to 5, where $\tau = 4$ days is the superiority null hypothesis of no difference between approaches.

Figure 8 shows the statistical power for non-inferiority as a function of the difference in absolute error between approaches (in days) and sample size. A horizontal reference line is drawn at 95% power. Under our assumptions, at a 0 difference in absolute errors between approaches, sample sizes of 200 or more have power in excess of 95%.

Figure 9 shows the statistical power for superiority as a function of the difference in absolute error between approaches (in days) and sample size. At the null hypothesis of 0 difference, the statistical power is approximately 5%, regardless of sample size (i.e., this is a valid statistical test). At a -0.5-day difference in absolute error (i.e., the FAMLI Technology estimated GA reduces random error by 1/2 day over standard approach), a sample size of 200 has less than 60% power, while a sample size of 400 has 80% power. Figure 10 shows the expected 95% CI as a function of the difference in absolute error between approaches (in days) and sample size.

In conclusion, we settle on a sample size of 400 women for the FAMLI study. Select numeric results are also shown in Table 4.

Table 4: Statistical power for non-inferiority and superiority, by difference in absolute error, and sample size *

T	Days	Statistical Power, %					
		Non-inferiority			Superiority		
		N=200	N=300	N=400	N=200	N=300	N=400
1.00	-2.22	0	0	0	100	100	100
1.25	-2.06	2	1	1	100	100	100
1.50	-1.89	9	10	12	100	100	100
1.75	-1.72	28	40	49	100	100	100
2.00	-1.53	60	75	86	100	100	100
2.25	-1.35	83	94	98	100	100	100
2.50	-1.16	95	99	100	100	100	100
2.75	-0.97	99	100	100	99	100	100
3.00	-0.77	100	100	100	89	98	100
3.25	-0.58	100	100	100	66	83	92
3.50	-0.38	100	100	100	34	47	59
3.75	-0.20	100	100	100	12	15	18
4.00	0.00	100	100	100	6	5	6
4.25	0.19	100	100	100	11	13	16
4.50	0.38	100	100	100	28	39	50
4.75	0.59	100	100	100	53	68	80
5.00	0.78	98	100	100	74	89	95
5.25	0.98	91	98	100	89	97	99
5.50	1.18	72	87	94	96	99	100
5.75	1.38	46	64	75	98	100	100
6.00	1.58	26	33	42	100	100	100

* Monte Carlo simulation error < 2%

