6.8.3 Analysis plan

For each woman, we will determine the estimated GA based on the initial first trimester visit, which will be our reference value. Then, for each approach, we will calculate the estimated GA and the difference between this estimate and the reference value. In a primary analysis, we will compare the mean absolute errors for the different approaches. The approach with smaller mean absolute error is preferred. In secondary analyses, we will compare the root mean squared errors for the different approaches.

Because approaches are conducted on all women, comparisons of approaches are naturally controlled for all possible time fixed confounding factors. To account for differential loss to follow up, if loss to follow up exceeds 9%, and possible resultant selection bias, we will employ inverse probability of censoring weights.³ Censoring weights will be estimated using a pooled logistic regression model fit by maximum likelihood.⁴ Continuous covariates will be included using restricted quadratic splines.⁵

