The Diagnostic Accuracy (DXA) Study primary outcome is the mean difference in absolute errors in gestational age assessment for the index test versus the clinical reference standard (expert biometry) conducted in the primary evaluation window (visit 1), defined in the protocol as between 14 $\frac{0}{7}$ and 27 $\frac{6}{7}$ gestational weeks, inclusive. The absolute errors, in days, for the index test and expert biometry are measured with respect to the gold standard assessment taken prior to 14 weeks of gestation. We will estimate a Wald-type 95% confidence interval for this difference. Specifically, let m be the mean of the difference in absolute errors for each participant (i.e., $m = n^{-1} \sum_{i=1}^n |y_{1(i)}| - |y_{2(i)}|$, where $y_{j(i)}$ is the error, in days from gold standard, for method j and participant i), and σ be the standard error of m , then the 95% confidence interval is given by $m \pm 1.96\sigma$. A negative or positive mean difference whose 95% confidence interval does not include zero indicates the index test is superior or inferior to expert biometry, respectively. A difference whose 95% confidence interval is contained in the prespecified equivalence range of -2 to 2 days indicates the index test is equivalent to expert biometry. To establish equivalence, two one-sided statistical tests on the difference between the mean absolute error of the index test (μ_t) and the mean absolute error the clinical reference standard (μ_r) will be carried out based on a predefined margin $c = 2$ days i.e. $H_{01}: \mu_t - \mu_r \leq -c$ and $H_{02}: \mu_t - \mu_r \geq c$.¹

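### Protocol 6.8.2 allows superiority to be declared without a direction, including for a confidence interval reaching above +2 days, and Table 4 gives directional names to two direction-blind quantities

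*Protocol*

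**What the plan says.** Protocol 6.8.2 sets c = 2 days and gives two rules for the 95% CI of the difference in mean absolute error (MAE).

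- If the CI lies completely inside (−c, c), "then we declare non-inferiority (or equivalence to bound c), with type 1 error 2.5"%.
- If it does not, because the lower end is below −c or "the upper end is larger than c , then we may declare superiority, with type 1 error 5"%. The reason given is that a zero difference would then be excluded.

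The same section fixes the sign. A difference of −0.5 day is glossed as "the FAMLI Technology estimated GA reduces random error by 1/2 day over standard approach". The random error τ = 4 "is the superiority null hypothesis of no difference between approaches", so rows of Table 4 with τ above 4 are those where the index test is worse. Of the superiority test the section says: "At the null hypothesis of 0 difference, the statistical power is approximately 5%, regardless of sample size". Table 4 is titled "Statistical power for non-inferiority and superiority, by difference in absolute error, and sample size".

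Protocol 6.8.3 adds: "The approach with smaller mean absolute error is preferred".

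The SAP's primary-outcome paragraph defines the difference as index minus reference and states: "A negative or positive mean difference whose 95% confidence interval does not include zero indicates the index test is superior or inferior". Negative goes with superior and positive with inferior. It calls containment in −2 to 2 days equivalence.

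**The concern.** There are two separate matters.

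First, the 6.8.2 rule names the upper end explicitly and attaches superiority to it. Take a CI of (1.2, 2.1) days. Read literally, the protocol permits a superiority claim for the index test, while the SAP calls the same result inferior. This is the decision rule for the primary comparison, and the documents do not say which text governs.

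Second, Table 4's column names do not match what the columns contain. A reader taking power from the table could read 95% at +0.78 days as a strong chance of showing the index test better, and 0% at −2.22 days as failure of a test that is clearly better.

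**Working it through.** **1. What Table 4's columns are.** Let d be the true difference (index minus biometry), s the paired SD and SE = s/√N. The two candidate direction-blind definitions are:

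- exclusion of zero: Φ(d/SE − 1.96) + Φ(−d/SE − 1.96)
- containment in (−2, 2): Φ((2 − d)/SE − 1.96) − Φ(−(2 + d)/SE + 1.96), or 0 if negative

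The documents do not state s. Using Table 4's own Days column for d and fitting one s per row, these two formulas match all 126 printed cells to within 2 percentage points. So the superiority column is two-sided exclusion of zero, and the non-inferiority column is containment.

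**2. Direction of the superiority column, N=400, inside the stated τ range of 1 to 5.**

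| τ | d (days) | fitted s | SE = s/20 | d/SE | Table 4 | lower limit > 0: Φ(d/SE − 1.96) | upper limit < 0: Φ(−d/SE − 1.96) |
|---|---|---|---|---|---|---|---|
| 4.25 | +0.19 | 3.95 | 0.198 | 0.96 | 16% | 15.9% | 0.2% |
| 4.50 | +0.38 | 3.90 | 0.195 | 1.95 | 50% | 49.5% | 0.0% |
| 4.75 | +0.59 | 4.17 | 0.209 | 2.83 | 80% | 80.8% | 0.0% |
| 5.00 | +0.78 | 4.25 | 0.213 | 3.67 | 95% | 95.6% | 0.0% |

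The conclusion does not depend on the fitted s. For any s, the chance that the upper limit falls below zero is at most 2.5% when d is positive. At d = 0 it is 2.5% in each direction, which together give the 5% (printed as 6% at N=400).

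**3. The non-inferiority column, N=400.** A one-sided rule needs only an upper limit below +2: Φ((2 − d)/SE − 1.96).

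| d (days) | Table 4 | upper limit < +2 |
|---|---|---|
| −2.22 | 0% | 100% |
| −1.89 | 12% | 100% |
| −1.72 | 49% | 100% |
| −1.53 | 86% | 100% |

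At −2.22 days, even s = 7 gives (2 + 2.22)/0.35 − 1.96 = 10.1, so the result is again insensitive to s. At zero difference both definitions give 100%.

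**4. What the SAP calls a CI with an upper end above +2.** Such a CI can include zero only if its full width exceeds 2 days, so its half-width exceeds 1. At N=400 that requires s above 20/1.96 = 10.2 days. The fitted s never exceeds 4.73, giving a half-width of 1.96 × 4.73/20 = 0.46. In a simulation from the protocol's printed inputs (20,000 replicates per row), the largest half-width at N=400 was 0.51, and no CI outside (−2, 2) included zero at any τ or N. As a check on other data, Protocol 4.1.1 reports a CI for 249 exams whose half-width is 0.7 if read as −1.3 to 0.1. Scaled to 400 it is 0.7 × √(249/400) = 0.55, still below 1. At the planned precision, then, a CI reaching above +2 is one the SAP labels inferior.

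**5. How often the wrong-direction trigger fires.** Take 100 minus the printed containment figure in rows with positive d. At N=400 it is 0% up to τ = 5.25, then 6%, 25% and 58% at τ = 5.50, 5.75 and 6.00, which lie outside the stated range of 1 to 5. At τ = 5 it is 2% for N=200 and 0% for N=300 and N=400.

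**The case against.** The strongest reply is that the analysis is properly defined elsewhere. Section 6.8.2 is the sample-size section. Section 6.8.3 says the approach with the smaller MAE is preferred, and the SAP states the directional rule in full. The no-difference null and the 5% error rate point to an ordinary two-sided test, loosely worded, in which whichever method has the smaller MAE wins. This stands, and it is why the practical risk is small. It does not put a sign into the 6.8.2 sentence, and it does not correct the non-inferiority label.

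On that label, 6.8.2 defines its rule as containment and adds the equivalence wording in parentheses. The −2.22-day row also prints 100% superiority beside the 0%, and signed differences accompany every percentage. So the label is partly disclosed rather than hidden.

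The documents do not support four stronger readings:

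- **That the SAP calls every CI with an upper end above +2 inferior.** It requires the CI to exclude zero as well; (−0.5, 2.5) would be inconclusive. The statement holds only at the planned precision.
- **That Table 4 repeats the fault in the 6.8.2 rule.** It does not apply that rule. Requiring the CI to leave (−2, 2) would give about 0% at zero difference, not the printed 5 to 6%.
- **That containment and exclusion of zero contradict each other.** Both can hold: at τ = 3.00 and N=400 Table 4 prints 100% for each.
- **That the sample size is undermined.** The power claim at zero difference is the same under either definition.

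**Conclusion.** The point holds as a minor error of wording and labelling. The 6.8.2 rule permits a superiority claim in the wrong direction, and at the planned precision the SAP gives the opposite label to the same CI. By Table 4's own figures at N=400, this would arise only from τ = 5.5. The table's superiority percentages at positive differences are power to show the index test worse, and its non-inferiority column is equivalence.

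The printed percentages are taken from Table 4. Direction and the one-sided figures rest on a normal approximation with a fitted SD, but they follow from the sign of the difference for any plausible SD. The simulation assumes independent errors for the two methods, which the documents do not state, and it does not reproduce every cell (at τ = 2.00 and N=400 it gives 95.0% containment against the printed 86%). It is used here only for the CI half-width and for whether zero is included.

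**What to change.** (a) In Protocol 6.8.2, replace the sentence on what follows when the CI is not contained in (−c, c) with the SAP's rule for the two-sided 95% CI of index minus biometry MAE: superior if the upper limit is below 0, inferior if the lower limit is above 0, equivalent if the CI lies inside (−2, 2).

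(b) Use equivalence for containment throughout 6.8.2: the opening sentences, the paragraph on the simulation target, the description of Figure 8, and Table 4's title and column. Label the other column, and the description of Figure 9, as two-sided difference from zero. Add a note that rows with positive Days give power to show inferiority.

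The cost is wording edits in several places of one section. No simulation needs rerunning, and the SAP, estimator, CI, margin and N=400 stay as they are.

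### Does Protocol section 6.8.2 overstate superiority power by equating a half-day MAE gain with a half-day fall in random error?

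*Protocol*

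**What the plan says.** Section 6.8.2 of the Protocol simulates both methods with a common intercept and slope against the enrolment gestational age. The index test is taken to have properties "similar to standard biometry, but reduces the random error", a quantity labelled τ, and τ = 4 "days is the superiority null hypothesis of no difference between approaches".

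The paragraph on Figure 9 sets the effect at -0.5 day of absolute error and explains it in a parenthesis as "the FAMLI Technology estimated GA reduces random error by 1/2 day over standard approach". It then states that "a sample size of 200 has less than 60% power, while a sample size of 400 has 80% power".

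Table 4, titled "Statistical power for non-inferiority and superiority, by difference in absolute error, and sample size", prints τ and the signed difference in days as separate columns, for τ from 1.00 to 6.00. The text on the superiority test adds: "At the null hypothesis of 0 difference, the statistical power is approximately 5%, regardless of sample size". Earlier in the section a superiority claim is justified without reference to direction, "because the null hypothesis for superiority (i.e., a 0-difference) would be excluded from this observed 95% CI".

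The SAP supplies the direction in its primary-outcome paragraph. It takes the sign of the mean difference, below or above zero, and says that one whose "confidence interval does not include zero indicates the index test is superior or inferior to expert biometry, respectively".

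**The concern.** Two things look wrong.

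First, the parenthesis appears to treat two scales as one. If random error means τ, as the section labels it, a half-day reduction is τ = 3.50. Table 4 gives that row 59% power at N=400, not 80%. A reader who takes the parenthesis literally would put the chance of missing such an improvement at 20%, when the table implies 100 - 59 = 41%.

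Second, the columns headed superiority fall to 6/5/6% at τ = 4.00 and rise again to 100% at τ = 6.00, where the difference is +1.58 days against the index test. Read by their heading alone, they seem to promise high power to show superiority for a method that is worse.

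If either point reflected a wrong calculation, the superiority argument for choosing 400 rather than 200 women would be in doubt.

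**Working it through.** **Inputs (Protocol section 6.8.2).** Enrolment gestational age x: 74.5 ± 10.5 days. Adjusted follow-up age: mean 75.6 days. Regression: -7 + 1.1x, residual SD 4 days. Table 4 rows for N=200/300/400:
- τ = 3.25: difference -0.58 day, superiority power 66/83/92%
- τ = 3.50: difference -0.38 day, superiority power 34/47/59%

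**Step 1: reproduce the stated power.** Interpolate Table 4 linearly at -0.50 day.
- Weight = (0.58 - 0.50)/(0.58 - 0.38) = 0.08/0.20 = 0.4
- τ = 3.25 + 0.4 × 0.25 = 3.35
- N=400: 92 - 0.4 × (92 - 59) = 78.8% (82.5% if interpolated on the probit scale)
- N=200: 66 - 0.4 × (66 - 34) = 53.2%

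Both agree with the text: 80% at 400 and below 60% at 200.

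**Step 2: simulate the stated model.** Each method's error is a + 0.1x plus normal noise, with SD 4 for biometry and τ for the index test. The interval is the paired m ± 1.96 SE, with N=400 and 4,000 to 10,000 replicates per run. Two intercepts are consistent with the rounded inputs:
- a = -7, as printed
- a = -6.35, which matches the mean shift: 75.6 - 74.5 = 1.1, and 1.1 - 0.1 × 74.5 = -6.35

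| τ | Simulated MAE difference | CI wholly below 0 | Compare |
|---|---|---|---|
| 3.35 | -0.48 to -0.50 | 81–86% | text: 80% at -0.5 day |
| 3.50 | -0.37 to -0.38 | 57–63% | Table 4: 59% |

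So 80% is right for -0.5 day of MAE, and 59% is right for τ = 3.50. An MAE gain of half a day needs τ to fall by 4 - 3.35 = 0.65 day.

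**Step 3: what the parenthesis can mean.** Intercept and slope are shared, so in this model any MAE gain comes from smaller random error. If random error is taken as its average size in days, E|N(0, τ)| = 0.798τ. A half-day fall then needs a drop in τ of 0.5/0.798 = 0.63, to about 3.37. That is almost the τ of 3.35 found in step 1.

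**Step 4: rows with τ above 4, N=400.**

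| τ | Table 4 difference | Printed superiority | CI wholly below 0 | CI wholly above 0 |
|---|---|---|---|---|
| 4.25 | +0.19 | 16% | 0.1–0.2% | 17–19% |
| 4.50 | +0.38 | 50% | 0.0% | 49–55% |
| 4.75 | +0.59 | 80% | 0.0% | 81–86% |
| 5.00 | +0.78 | 95% | 0.0% | 96–98% |
| 6.00 | +1.58 | 100% | 0.0% | 100% |

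The printed entries are two-sided rates of excluding zero. At τ = 3.50 and 3.35 the wrong-direction share is at most 0.01%, so the entries for a better index test can be read as superiority power.

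**Limit of the check.** The simulation does not match every non-inferiority cell: at τ = 2.00 and N=400 it gives 94–98% against a printed 86%. Nothing here depends on that cell.

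**The case for a change.** The best case for an edit is that the section ties random error to τ just before the parenthesis, and its power scenarios are indexed by τ. A reader who follows that definition is told 80% where the table says 59%. Correcting one parenthesis and one heading would cost almost nothing and would keep the superiority claim from being misquoted.

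The first part stands: on the section's own labelling the parenthesis is loose, and the average-size reading in step 3 is charitable rather than stated. But the sentence gives its effect first, and plainly, as a difference in absolute error. That is the scale of the primary outcome and of Table 4's title. Table 4 prints τ beside the difference in days, so a reader can put the scale right at once.

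The second part is weaker. The text reports about 5% power at the null, which already shows that the test is two-sided. Reporting such a test's rejection rate under the test's name is ordinary practice, and the signed difference shows the direction in every row. The heading does not contradict the SAP: the table gives a rejection rate under an assumed truth, while the SAP interprets an observed interval.

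**Conclusion.** No change follows; this is a clerical slip in explanatory text. The power the Protocol relies on is right on the scale it names: about 79% by linear interpolation and 81 to 86% by simulation, against the stated 80% at -0.5 day of MAE and N=400. The 59% applies to a half-day fall in τ, which no endpoint, hypothesis or decision uses. The entries for τ above 4 are valid two-sided rates, and analysts applying the SAP's sign rule would report such results as inferior. The primary equivalence test does not touch this point: Table 4 gives 100% non-inferiority power at zero difference for all three sample sizes.

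The conclusion rests on the model in section 6.8.2 (normal errors, shared bias, biometry residual SD 4 days) and on Table 4 as printed. The spread between 81 and 86% comes mainly from rounding in the reported regression coefficients. Figure 9, which the text cites for these powers, was not available to check.
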